10.3.1. Safety Analyses

All safety analyses will be based on the Safety Population.

Endpoint	Statistical Analysis Methods
Adverse events (AEs)	The proportion of participants reporting AEs will be tabulated by treatment and by cohort. AEs will also be tabulated by severity and relationship.
Clinical laboratory	Laboratory results will be included in the reporting of this study for hematology, clinical chemistry, and urinalysis. Based upon laboratory normal ranges, the laboratory test results will be categorized according to the normal range as low (below the lower limit), normal (within the normal range) and high (above the upper limit). Summary statistics for change from baseline will also be tabulated.
Electrocardiogram (ECG)	The ECG parameters of PR, QRS, QT, QTc, QTcF and HR (bpm) will be reported. Overall assessment of ECG (Investigator's judgment) will be recorded as Normal, Abnormal - Not Clinically Significant and Abnormal - Clinically Significant. Summary statistics for change from baseline will also be tabulated.
Telemetry	Overall assessment of Telemetry (Investigator's judgment) will be recorded as Normal, Abnormal - Not Clinically Significant and Abnormal - Clinically Significant.
Spirometry	% Predicted forced expiratory volume in 1 second (FEV1) and forced vital capacity (FVC) values will be tabulated for each timepoint.
Vital signs assessments	The following Vital Signs measurements will be tabulated: supine systolic and diastolic blood pressure, pulse rate, respiratory rate and temperature. Summary statistics for change from baseline will also be tabulated.
Monodose RS01 Device safety	Safety incidents reported from use of medical device will be tabulated.

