Repeat dose schedule to be followed for repeat dose cohorts in Parts 1 and 2 (other than Cohort A Part 1)

Procedure	Treatment Period, Days															
	-1	1	2	3	4	5	6	7	8	9	10	11	12	13	14	15
Inclusion and exclusion criteria	Х															
Brief physical examination, oral examination	Х															Χ
Substance testing (drugs, alcohol, tobacco1)	Х															
Inhaler device training ²	Х															
Serum pregnancy test in women	Х															
Admittance to clinic	Х															
Randomization	X3															
Discharge																X ⁴
Dosing procedure training with bystanders		X 5														
Haematology, clinical chem and urinalysis (include liver chem) ⁶	Х							Χ								Χ
Spirometry		X ⁷		X8			X8					X8			X ⁷	
Telemetry (starting 30 min pre-morning dose and continuous at least 4h post-morning dose)		Х						Х						X9		
12-lead ECG and vital signs ¹⁰	XXX	Χ		Х	Χ		Х	Χ	Х		X11		X11			
CCI15106-IP or placebo treatment BID, device incident assessment BID ¹²		Х	Х	Х	Х	Х	Х	Х	Х	Х	Х	Х	Х	Х	Х	
PK blood sample ¹³		Χ	Χ		Χ		Χ		Χ		Χ		Χ		Χ	Χ
BAL	X14															
Urea blood sample	X15															
AE review	←========→															
SAE review	←======== →					\rightarrow										
Concomitant medication review	←						\rightarrow									

- 1. Tobacco test to be performed only in healthy participants
- 2. Day -1 inhaler training may be done on Day 1 instead, before the first dose administration. Other time-points may be added per investigators discretion.
- 3. Can be performed on Day 1 prior to dosing
- 4. After all procedures and assessments are complete
- 5. To be done only in Cohort(s) where bystanders are present. Can be performed on Day -1 instead, if desired. Other time-points may be added per investigators discretion.
- 6. To be drawn fasting (for at least 8 h)
- 7. To be performed at the following timepoints in the mornings only: pre-dose, and 0.25 (in participants with COPD only), 0.5, 1, 4 h post-dose
- 8. To be performed at the following timepoints in the mornings only: pre-dose and 4 h post-dose

2016N290366_02 **CONFIDENTIAL** 205822

- 9. Telemetry may be performed on Days 11 or 12 instead, not to coincide with the BAL procedure.
- 10. ECG and vital signs to be obtained 2 h after the morning dose
- 11. When BAL is performed, vital signs and ECG will be performed before and after the procedure and oxygen saturation will be measured continuously.
- 12. For cohort with bystanders, BID doses may have ± 1.5 h window.

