7.7. Concomitant Therapy

7.7.1. Permitted Medications and Non-Drug Therapies

Paracetamol or Acetaminophen, at doses of ≤ 2 grams/day is permitted.

Medications associated with the BAL procedure are permitted, but these medications are to be disclosed to the Sponsor prior to dosing any participants.

Participants with COPD taking medications for any chronic conditions have to be on stable doses for 4 weeks prior to screening and until after completion of the treatment period.

Salbutamol is administered 15 to 30 min prior to spirometry at screening for diagnostic purposes. Short-acting bronchodilators should not be used from 6 h prior to each morning dose administration until 4 h after that dose. If they become medically necessary during that time, short-acting bronchodilators may be administered as needed by the clinical staff only and their use must be documented.

For participants with COPD, use of long-acting bronchodilators is allowed, but their use must be modified twice during the study as follows: at screening and on Day 1, they must not be taken for at least 2 h prior to spirometry.

Other concomitant medication may be considered on a case by case basis by the investigator in consultation with the Medical Monitor.

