7.7.2. Prohibited Medications and Non-Drug Therapies

Participants are not allowed to take oral corticosteroids from 4 weeks prior to screening and for the duration of the study.

For participants with COPD, self administration of short-acting inhaled bronchodilators is not allowed at screening, from 4 h prior to spirometry until spirometry is completed. Self administration of short-acting inhaled bronchodilators is not allowed during treatment period from 6 h prior to each morning dose administration until 4 h after that dose.

Didanosine and azathioprine are not allowed.

Except as permitted in Section 7.7.1, participants must abstain from taking prescription or non-prescription drugs (including vitamins and dietary or herbal supplements), within 7 days (or 14 days if the drug is a potential enzyme inducer) or 5 half-lives (whichever is longer) prior to the first dose of study medication until completion of the follow-up visit, unless in the opinion of the Investigator and sponsor the medication will not interfere with the study.

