9.4.5. Spirometry

- Spirometry (FEV1 and FVC) will be performed at time points specified in the SoA (Section 2). Further tests should be performed, at the discretion of the investigator, if the participant has symptoms that could suggest bronchospasm.
- Spirometry manoeuvres will be conducted according to ATS/ERS 2005 spirometry standards [Miller, 2005]. The greatest FEV1 and the greatest FVC from 3 technically acceptable and reproducible manoeuvres will be recorded.
- For participants with COPD, at screening, 400 µg salbutamol will be administered 15-30 minutes prior to performing spirometry. FEV1 and FVC percent predicted values will be derived using the Global Lung Function Initiative reference values [Quanjer, 2012].

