10.3. Statistical Analyses

The analysis and reporting of Part 1 may be conducted prior to the completion of Part 2. For all parts, the analysis and reporting will be performed after the datasets are authorized and released for reporting.

Data will be listed and summarized according to GSK reporting standards, where applicable. Listings will be sorted by cohort, participant and time; summaries will be presented by cohort, treatment, and time.

Descriptive summaries will include n, mean, standard deviation (SD), median, minimum, and maximum, geometric mean with associated 95% confidence interval (CI), and the between-participant coefficient of variation (%CVb) for continuous variables, n and percent will be used as summary statistics for categorical variables.

Baseline or pre-dose assessment is the last available assessment prior to time of the first dose unless it is specified otherwise. If there are multiple assessments collected at the same scheduled time, the average of these assessments will be used. For tabulated safety summaries, only the scheduled assessments will be included in the summary tables.

Version 9.1 or higher of the SAS system will be used to analyze the data as well as to generate tables, figures, and listings.

Complete details will be documented in the RAP.

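### The spirometry summary can understate an acute FEV1 fall in a rescued participant, because it leaves out the symptom-triggered test and keeps the later scheduled reading

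*Protocol*

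**What the plan says.** Spirometry is one of the primary safety endpoints (protocol Section 4). Four rules decide what its summary will show.

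- Section 10.3.1, spirometry row: "Predicted forced expiratory volume in 1 second (FEV1) and forced vital capacity (FVC) values will be tabulated for each timepoint". No exception is made for readings taken after rescue.
- Section 10.3: "For tabulated safety summaries, only the scheduled assessments will be included in the summary tables".
- Section 9.4.5: "Further tests should be performed, at the discretion of the investigator, if the participant has symptoms that could suggest bronchospasm".
- Section 7.7.1: "Short-acting bronchodilators should not be used from 6 h prior to each morning dose administration until 4 h after that dose". The same section allows an exception on medical grounds within that period: "short-acting bronchodilators may be administered as needed by the clinical staff only and their use must be documented". Section 7.7.2 repeats the restriction for self-administration by participants with COPD.

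The Schedule of Activities (Section 2) fixes the scheduled readings. In the repeat-dose cohorts, Days 1 and 14 have "pre-dose, and 0.25 (in participants with COPD only), 0.5, 1, 4 h post-dose". Days 3, 6 and 11 have a reduced set: "To be performed at the following timepoints in the mornings only: pre-dose and 4 h post-dose". Cohort A Part 1 uses the same reduced set on Days 8, 11 and 16.

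Section 10.3 leaves complete analysis details to the Reporting and Analysis Plan (RAP), which was not available for this review.

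**The concern.** The restricted period runs through the 4 h reading, so it covers every scheduled post-dose spirometry test. That suggests the protocol regards bronchodilator use as affecting these readings. Rescue in the same period is nevertheless possible, and it would be prompted by the outcome being measured.

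A participant whose airways react may then contribute to the summary only a value obtained after bronchodilation, while the test that recorded the fall stays outside it. Which reading is kept depends on whether the participant reacted, and the error runs towards no effect.

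This matters because Section 3.3.1 names bronchospasm and deterioration of lung function in COPD as known risks of aerosolised ribavirin and offers frequent spirometry as a mitigation. Section 5.5 also puts spirometry in the minimum data set for choosing the Part 1 Cohort B dose.

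**Working it through.** **The plan's own figures.** None is given for spirometry or rescue. The only computed figures in the statistical section are the Section 10.1 probabilities of at least one adverse outcome, 1 - (1 - p)^n. They reproduce: n = 6 gives 0.265 and 0.738 (stated 26% and 73%), and n = 12 gives 0.460 and 0.931 (stated 46% and 93%), for p = 5% and 20%. They are not in dispute and say nothing about the size of this problem.

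**Which reading survives.** Take a participant on repeat-dose Day 6 who has symptoms soon after the morning dose, is tested, and is then given a bronchodilator by staff before 4 h.

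1. Pre-dose reading: scheduled, enters the summary.
2. Symptom-triggered reading (Section 9.4.5): not scheduled, kept out by Section 10.3.
3. 4 h reading: scheduled and after rescue, enters the summary under Section 10.3.1.

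The summary for that morning therefore holds no post-dose, pre-rescue value for this participant.

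**Where it can happen.**

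| Mornings | Scheduled post-dose readings | After an early rescue |
|---|---|---|
| Repeat-dose Days 3, 6, 11 (3 of 5 spirometry mornings) | 4 h only | No scheduled pre-rescue reading |
| Cohort A Part 1 Days 8, 11, 16 | 4 h only | No scheduled pre-rescue reading |
| Repeat-dose Days 1, 14, COPD | 0.25, 0.5, 1, 4 h | Rescue after 0.25 h leaves that reading intact; the other 3 of 4 follow rescue |

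**Illustrative size.** Active group sizes come from Section 10.1: n = 12 in each Cohort B and n = 6 in Cohort A Part 1. The documents give no fall, rescue rate or degree of reversal, so the following are assumptions. Let k of n active participants fall by d points of % predicted FEV1, let rescue return them exactly to baseline, and suppose the fall would otherwise have lasted to the affected reading. Then

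hidden fall in the mean = k × d / n.

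| n | k | d = 10 | d = 20 |
|---|---|---|---|
| 12 | 1 | 10/12 = 0.8 | 20/12 = 1.7 |
| 12 | 3 | 30/12 = 2.5 | 60/12 = 5.0 |
| 6 | 1 | 10/6 = 1.7 | 20/6 = 3.3 |

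If the post-rescue value is 5 points above baseline, k = 1 and d = 20 give (20 + 5)/12 = 2.1 points, or (20 + 5)/6 = 4.2 points. The pre-dose value is unaffected, so the arithmetic is the same for a mean level and a mean change.

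The tabulated minimum (Section 10.3 lists it among the summary statistics) also loses the participant's low value. In groups this small, that may matter more than the shift in the mean.

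**The case against.** The strongest reply is that handling of values after a concomitant medication is ordinary RAP detail, that no sentence says post-rescue readings are pooled without a flag, and that as-measured summaries are legitimate in a descriptive Phase 1 study. Silence on flagging would indeed be no finding. But the protocol is not silent on selection: it states that only scheduled readings enter the summary, and that rule, set beside Section 9.4.5, excludes the reading taken because of symptoms. The RAP may add handling, but it would have to depart from this rule to bring that reading in.

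A reader might infer that the plan masks the drug's main lung risk. The documents do not support that. Bronchospasm is tabulated as an adverse event by treatment and cohort and by severity and relationship (Section 10.3.1). Individual data are listed by participant and time (Section 10.3), and rescue use must be documented (Section 7.7.1). Two or more related grade 3 respiratory events within a dose level halt the study (Section 8.1.3). Early scheduled readings on single-dose days and on repeat-dose Days 1 and 14 may also show the fall. These routes make the event visible, although they do not repair the spirometry table.

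Two further points stand. The sizes above rest on assumed full reversal and on a fall that would have persisted. And a brief early fall on a 4 h-only morning would be missed by the scheduled reading even without rescue, which is a feature of the schedule.

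**Conclusion.** The concern holds for one table. As written, Sections 9.4.5, 10.3 and 10.3.1 keep the symptom-triggered reading out of the spirometry summary and retain a later scheduled reading that may follow a bronchodilator. The summary can therefore understate an acute fall in a rescued participant, chiefly on mornings with a single 4 h post-dose reading. The lung risk is understated in that table and remains visible elsewhere.

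The size cannot be derived from the documents. Under the assumptions stated, one rescued participant hides 0.8-1.7 points of the mean in a group of 12, or 1.7-3.3 points in a group of 6. The correction should be made because spirometry is a primary safety endpoint and the change is cheap.

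**What to change.** Change the analysis only; the rescue rule stays as it is. In Section 10.3.1, for treatment-period spirometry (so that the screening test, done by design after salbutamol, is not caught):

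1. Keep the as-measured table by timepoint, and flag each reading taken after a short-acting bronchodilator given that morning.
2. Add, for all participants alike, a summary of the lowest post-dose FEV1 and FVC % predicted before any rescue on each dosing morning. Include unscheduled tests, as a stated exception to the scheduled-only rule in Section 10.3.
3. Tabulate by treatment and cohort the number of participants given rescue within 4 h of a dose, so that anyone with no pre-rescue reading is counted and does not simply disappear.
4. Confirm that the time of rescue is recorded. Section 7.7.1 requires documentation of use but does not mention time, and items 1 to 3 need it.

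Keeping the lowest-value summary separate avoids mixing worst-case and as-measured values in one mean. The cost is one or two extra tables and a check of the data collection form.

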4. OBJECTIVES AND ENDPOINTS

Objectives			Endpoints		
Pri	mary		·		
•	To investigate the safety and tolerability of CCI15106-IP following single and repeat escalating doses in healthy participants and participants with moderate COPD.	•	Adverse events (AEs), clinical laboratory, electrocardiogram (ECG), telemetry, spirometry, and vital signs assessments.		
•	To determine systemic PK of CCI15106 following single and repeat escalating doses of CCI15106-IP in healthy participants and participants with moderate COPD.	•	Derived systemic PK parameters of CCI15106: Single dose: area under the curve (AUC) from time zero to the time of last quantifiable concentration (AUC[0-last]), concentration at maximum (Cmax), time of maximum concentration (tmax), AUC from time zero to infinity (AUC[0- ∞]) elimination half-life (t1/2), clearance (CL/F), as data permit. Repeat dose: AUC from time zero to end of dosing interval (AUC[0- τ]) (τ =12 hours [h] for twice daily dose regimen), Cmax, tmax, elimination half-life (t1/2) as data permit.		
•	To evaluate potential inhalation exposure of bystanders to airborne CCI15106 during self-administered dosing of participants.	•	Concentration of CCI15106 in plasma of bystanders 15-20 minutes (min) after dosing (at predicted tmax) and amount of CCI15106 accumulated on filters fitted on bystander over 15 min after dosing.		
•	To evaluate the distribution and persistence of airborne CCI15106 in room air post-dosing.	•	Amount of CC15106 in room air assessed by measuring amount of CCI15106 accumulated over 20 and 60 min intervals during and immediately post-dosing on filters fitted on stationary pumps placed in the room.		
Se	condary				
•	To determine the concentration of CCI15106 in the lung of healthy participants and participants with moderate COPD following repeat dosing of CCI15106-IP.	•	Concentrations of CCI15106 in lung epithelial lining fluid (ELF) assessed by bronchoalveolar lavage (BAL).		
•	To investigate the performance of the Monodose RS01 device for the administration of CCI15106-IP in healthy participants and participants with moderate COPD.	•	Device safety and performance parameters, including medical device incidents reporting, as well as systemic PK and lung CCI15106 concentrations.		

Objectives	Endpoints		
Tertiary/Exploratory			
To assess dose proportionality of CCI15106-IP versus systemic PK parameters.	 Comparisons of doses administered and systemic PK parameters of CCI15106: AUC(0-24) or AUC(0-τ) and Cmax. 		

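### Spirometry is the only numeric primary safety measure planned without a change-from-baseline summary, so the tables will not show the size or spread of within-participant change after dosing

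*Protocol*

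**What the plan says.** Section 4 of the protocol gives the primary safety endpoints as "Adverse events (AEs), clinical laboratory, electrocardiogram (ECG), telemetry, spirometry, and vital signs assessments". Section 10.3.1 then sets out, row by row, how each is summarised.

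- Clinical laboratory, ECG and vital signs: each row ends with "Summary statistics for change from baseline will also be tabulated".
- The row for telemetry is purely categorical: "Overall assessment of Telemetry (Investigator's judgment) will be recorded as Normal, Abnormal - Not Clinically Significant and Abnormal - Clinically Significant".
- Spirometry: percent "Predicted forced expiratory volume in 1 second (FEV1) and forced vital capacity (FVC) values will be tabulated for each timepoint". Nothing further is said. The row is the same in all three protocol versions in the file.

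The general rules are in Section 10.3. The default reference is fixed as follows: "Baseline or pre-dose assessment is the last available assessment prior to time of the first dose unless it is specified otherwise". Presentation is described thus: "Listings will be sorted by cohort, participant and time; summaries will be presented by cohort, treatment, and time". Summary tables carry mean, SD, median, minimum and maximum, and take scheduled assessments only. The section closes with "Complete details will be documented in the RAP".

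In the Section 2 schedules, each spirometry day in the treatment period has a pre-dose reading. The lightest days in the repeat-dose schedule are described as "To be performed at the following timepoints in the mornings only: pre-dose and 4 h post-dose"; the fuller days add further post-dose readings within 4 h.

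**The concern.** The quantity of interest for an inhaled powder is how far a participant's lung function moves after the dose, compared with the same person just before it. Section 3.3.1 lists bronchospasm and deterioration of pulmonary function in COPD among the labelled effects of approved formulations, and names frequent spirometry as the monitoring tool. Section 5.5 puts spirometry in the minimum data set for choosing the Part 1 Cohort B dose. Yet this is the one numeric safety measure for which the plan summarises levels and not change.

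Percent-predicted levels differ widely between people; COPD entry alone spans 50% to just under 80% predicted FEV1. A table of levels by timepoint mixes that spread with any post-dose movement. A reader of the summary tables could not tell whether a lower post-dose mean reflects a small shift in everyone or a large fall in one person, nor how precisely the shift is estimated.

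**Working it through.** **1. Rows compared.** Of the six primary safety endpoints, four are numeric: laboratory, ECG, vital signs and spirometry. Three of these have change from baseline stated; spirometry does not. Adverse events and telemetry are categorical.

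**2. Are paired readings available?** Yes, from Section 2:
- Part 1 Cohort A: spirometry on Days 1, 3, 6, 8, 11, 16 and 19.
- Repeat-dose cohorts: Days 1, 3, 6, 11 and 14.
- Part 2 Cohort A: Day 1.

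Each of these days has a pre-dose reading and at least a 4 h post-dose reading.

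**3. Which reference?** The default baseline precedes the first dose. On later days, change from it combines the acute post-dose effect with day-to-day drift. In Part 1 Cohort A the same people receive 60 mg on Day 1, 120 mg on Day 3 and 30 mg BID on Days 6-19, so a later-day change from that baseline also carries any effect of earlier dose levels. The acute effect needs the same-day pre-dose value.

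**4. Scale.** The protocol gives no figure for spirometry; its only sample-size figures are chances of seeing at least one adverse outcome. The SDs below are assumptions, in percentage points of predicted FEV1: between-participant SDb 10-15 and within-participant SDw 4-5. From the protocol, n = 12 active in each Cohort B.

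- SE of a raw mean = √(SDb² + SDw²)/√12
- SE of mean same-day change = √2 × SDw/√12
- Variance ratio = (SDb² + SDw²)/(2 × SDw²)

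| SDb, SDw | SE, raw mean | SE, change | Variance ratio |
|---|---|---|---|
| 10, 4 | √(116/12) = 3.11 | 1.63 | 116/32 = 3.6 |
| 10, 5 | √(125/12) = 3.23 | 2.04 | 125/50 = 2.5 |
| 15, 4 | √(241/12) = 4.48 | 1.63 | 241/32 = 7.5 |
| 15, 5 | √(250/12) = 4.56 | 2.04 | 250/50 = 5.0 |

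The ranges are 3.1-4.6 for the raw mean, 1.6-2.0 for change, and a variance ratio of 2.5-7.5.

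**5. Cross-check from the entry range.** An even spread over 50-80% has SD 30/√12 = 8.66. Take this as the SD of a level and assume a pre/post correlation ρ. The 95% half-width is t × SD/√n for a level and t × SD × √(2(1−ρ))/√n for change.

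| n active | Level | Change, ρ = 0.80 | ρ = 0.90 | ρ = 0.95 |
|---|---|---|---|---|
| 6 | 9.1 | 5.7 | 4.1 | 2.9 |
| 12 | 5.5 | 3.5 | 2.5 | 1.7 |

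A 5-point fall shared by everyone would lower the mean by 5 points, but lies inside the level half-width at both sizes.

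**6. One participant.** Take 12 pre-dose values evenly spaced from 50 to 79.9 and let one mid-range participant fall by 20% of their own value (13.3 points). The mean goes from 65.0 to 63.8 and the SD from 9.8 to 10.4; the minimum and maximum stay at 50.0 and 79.9. In a change table the minimum would read −13.3.

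**The case against.** The strongest reply is that the protocol leaves full detail to the RAP, which is not shown. The spirometry row does not exclude a change summary, and the baseline rule allows a different reference to be specified. The choice of reference and scale is ordinary analysis-plan material. That is fair for the finer choices. It does not dispose of the point, because the protocol is not silent here: it fixes a method for each primary safety measure and gives this one the less informative method.

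A reader might also infer that an acute fall would be hidden altogether. The documents do not support that:
- Listings by participant and time put each person's pre-dose and post-dose values together, and with 6 or 12 active participants they can be read directly.
- With complete data, the difference between the pre-dose and post-dose means equals the mean change; what is lost is its spread and range.
- Symptoms suggesting bronchospasm prompt further spirometry (Section 9.4.5), although unscheduled readings do not enter the summary tables.
- Clinically significant abnormal safety assessments are adverse events (Appendix 4), and related grade 3 respiratory events in two participants at a dose level halt the study (Section 8.1.3).

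Two further objections stand in part. A mean change also dilutes a fall in a few people, so the minimum of the change and the individual largest falls matter as much as the standard error. And the weakness of a comparison with two placebo participants applies equally to change scores, so it is no argument for the fix.

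**Conclusion.** The point holds as an inconsistency in the planned summaries, not as a failure of safety detection. Spirometry alone among the numeric primary safety measures lacks a change summary, and the readings needed for one are already scheduled.

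The direction of the precision gain is secure wherever pre-dose and post-dose values in the same person correlate above 0.5, since the variance ratio is 1/(2(1−ρ)). Its size rests on SDs and correlations that the protocol does not give. If the between-participant SD were nearer 8.66, as an even spread over the COPD entry range implies, the ratio would be (75 + 25)/50 = 2.0 at SDw 5 and (75 + 16)/32 = 2.8 at SDw 4. The change is worth making, but no conclusion of the study depends on it alone.

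**What to change.** Keep percent-predicted FEV1 and FVC by timepoint, and add to the spirometry row of Section 10.3.1:

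- summary statistics for change in FEV1 and FVC from the same-day pre-dose value at each scheduled post-dose time;
- summary statistics for change of each later day's pre-dose value from the Day 1 pre-dose value, to show drift or a cumulative effect;
- a listing of each participant's largest post-dose fall on each spirometry day.

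State the same-day reference explicitly, since the Section 10.3 default would otherwise apply. In the repeat-dose cohorts, flag Day 11 post-dose values from anyone whose bronchoscopy was that morning, because the procedure falls between the two readings.

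The cost is a few extra tables and one listing. No new data, visits or procedures are needed.
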